**b) Consolidation Phases (Cohort 1 & 2)**

Analysis phase	Target day	Analysis time point (Week)			Consolidation Analysis time points (label)	Time interval (Consolidation days) h
Consolidation	1	ATEOI i +1	36	36	C Baseline	1
	15	ATEOI i +1	38	38	C Week 2	[1,22]
	29	ATEOI i +3	40	40	C Week 4	[23,36]
	43	ATEOI i +5	42	42	C Week 6	[37,50]
	57	ATEOI i +7	44	44	C Week 8	[51, 71]
	85	ATEOI i [contact]	C Week 12	[72, 99]
	last visit in consolidation phase	ATEOI i +12 e,j	49 f,j	49 g,j	EOC j	

e Analysis time point for Cohort 1 will be based on end date of the induction phase in the Table 2 a) above.

f Analysis time point for Cohort 1 will be based on end date of the induction phase in the Table 2 a) above.

g Analysis time point for Cohort 2 will be based on end date of the induction phase in the Table 2 a) above.

h Relative to Consolidation start date (see the Table 1).

i ATEOI = Analysis time point (Week) for EOI.

j End of consolidation (EOC) visit will be the last post baseline visit in the Consolidation phase.

**c) Follow-Up Phase (Cohort 1 & 2)**

Analysis phase (FU)	Target day	Analysis time point (Week)			Analysis time point (label)	Time interval (FU days) n
Follow-up	15	ATEOC o +1	50	50	FU Week 2	[1, 22]
	29	ATEOC o +3	52	52	FU Week 4	[23, 43]
	57	ATEOC o +7	56	56	FU Week 8	[44, 71]
	85	ATEOC o [contact]	FU Week 12	[72, 99]
	113	ATEOC o [contact]	FU Week 16	[100, 127]
	141	ATEOC o [contact]	FU Week 20	[128, 155]
	169	ATEOC o [contact]	FU Week 24	[156, 183]
	197	ATEOC o [contact]	FU Week 28	[184, 211]
	225	ATEOC o [contact]	FU Week 32	[212, 239]
	253	ATEOC o [contact]	FU Week 36	[240, 267]
	281	ATEOC o [contact]	FU Week 40	[268, 295]
	309	ATEOC o [contact]	FU Week 44	[296, 323]
	337	ATEOC o [contact]	FU Week 48	[324, + $\infty$ ]
	last visit in the study	999 k,p	999 l,p	999 m,p	EOS p	

k Analysis time point for Cohort 1 will be based on end date of the induction and consolidation phase.

l Analysis time point for Cohort 1 will be based on end date of the induction and consolidation phase.

m Analysis time point for Cohort 2 will be based on end date of the induction and consolidation phase.

n Relative to follow-up start date.

o ATEOC = Analysis time point (Week) for EOC.

p End of study (EOS) visit (last available data during the follow-up) will be the last visit in the study.

## 2.2. Baseline

### 2.2.1. Study Baseline

In general, the baseline assessment is defined as the last observed non-missing measurement before the date and time of the first administration of any of study treatments in the induction phase.

In case the first administration time is missing, the first observed measurement on Induction Day 1 will be used as the baseline measurement. If no observed measurement on Induction Day 1, the last observed measurement before Induction Day 1 will be used as the baseline assessment.

The baseline defined above is the study baseline and will be used for all analysis throughout the induction, consolidation and follow up phases.

### 2.2.2. Consolidation Baseline Timepoint

For the participants who receive PegIFN-  $\alpha$ 2a, the consolidation baseline assessment is defined as the date of first PegIFN-  $\alpha$ 2a intake. For the participants who did not receive PegIFN-  $\alpha$ 2a, the consolidation baseline will be defined as the date of any study agent intake after Max[Week 36 to 60 visit date] for Cohort 1 and the date of any study agent intake after Week 36 visit date for Cohort 2.

## 2.3. Analysis Sets

Due to a potential impact of future Coronavirus Disease 2019 (COVID-19) pandemics on the study data collection, study treatment adherence and study conduct, the modified treated (mTreated) analysis set and the modified intent-to-treat analysis (mITT) set are defined to target the estimation of the treatment effect without the pandemic-related influences.

If there is a relevant difference (5% of total population or more participants in total) from the ITT analysis vs the mITT analysis set, then, the mTreated, and mITT will be used. However, if there is less than 5% difference, then the Treated and ITT, will be used.

**Treated analysis set:** All participants who received at least 1 dose of study treatment within this ISA.

**Modified Treated analysis set (mTreated):** All participants who received at least one dose of study treatment, excluding participants who have no efficacy assessment for the primary endpoint (24 weeks after stopping all study treatment of the consolidation phase) because of COVID-19 or similar pandemics related reasons (e.g., missed visits due to travel restriction, shortage of lab kits at the planned visit, missed collection of blood sample at key time points for the primary analysis endpoint, etc.).

**Intent-to-Treat analysis set (ITT):** All participants who were randomized or enrolled and who received at least 1 dose of consolidation phase study intervention within this ISA.

**Modified Intent-to-Treat analysis set (mITT):** All participants who were randomized or enrolled and received at least one dose of the consolidation phase study intervention excluding those participants impacted by the pandemic defined as those participants who, because of COVID-19 or similar pandemics related reasons, withdrew prematurely from the study prior to FU Week 24 or had no efficacy assessment for the primary endpoint (24 weeks after stopping all study interventions of the consolidation phase). COVID-19 or similar pandemics related reasons may include for example missed visits due to travel restriction, shortage of lab kits at the planned visit, missed collection of blood sample at key time points for the primary analysis endpoint, etc.

**Safety analysis set:** All participants who received at least one dose of study intervention. Participants will be analyzed according to the study intervention they actually received.

**Per protocol analysis set (PP):** All participants in the ITT analysis set who do not have any of the selected major protocol deviations that may affect the assessment of efficacy in terms of the primary endpoint at 24 weeks after stopping all study interventions of the consolidation phase. The selected major protocol deviations for efficacy analysis purposes that will be used to identify the participants included in the PP set are described in Section 4.5 and [Attachment 1: Selected Major Protocol Deviations for Analysis Purposes](#). Participants will be analyzed according to the study intervention they were randomly assigned to.

**Pharmacokinetics analysis set (PK):** The PK analysis set is defined as subjects who have received at least 1 dose of any of the study interventions and have at least 1 valid blood sample drawn for PK analysis.

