## **Efficacy Analyses**

The primary efficacy analysis will be performed when all participants have completed FU Week 24 or discontinued earlier. The final analysis will be performed when all participants have completed the last study visit (FU Week 48) or discontinued earlier.

To evaluate the efficacy, the primary analysis set will be the intent-to-treat (ITT) population of Cohort 2: all participants who were randomized or enrolled and who received at least 1 dose of consolidation phase study intervention within this ISA will be included in the ITT population. The efficacy for Cohort 1 will be evaluated on the treated population set. A secondary analysis of efficacy will be performed combining the data pre- and post-Amendment 6, i.e. combining the data from participants who received PegIFN- $\alpha$ 2a but not JNJ-6379 in Cohort 1 with data of Cohort 2. The approach to combine data from the 2 cohorts will be described in detail in the Statistical Analysis Plan.

The baseline measurements are defined as the measurements taken closest to but before the first administration of study intervention on Day 1, unless otherwise specified.

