If a participant prematurely (before the end of the consolidation phase) discontinues JNJ-3989, the participant will enter the 48-week follow-up phase and complete the follow-up schedule as per the Schedule of Activities, unless the participant withdraws consent. If a participant prematurely discontinues PegIFN-α2a (before the end of the consolidation phase), treatment with JNJ-3989 and NA should be continued as planned. In case the participant withdraws consent, NA treatment may be continued or, in consultation with the sponsor, discontinued based on investigator judgement or completed based on the NA treatment completion criteria (see Section 6.6).

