# 9.4. Statistical Analyses

# 9.4.1. Efficacy Analyses

The primary efficacy analysis will be performed when all participants have completed FU Week 24 or discontinued earlier. The final analysis will be performed when all participants have completed the last study visit (FU Week 48) or discontinued earlier.

To evaluate the efficacy, the primary analysis set will be the ITT population (ie, for Cohort 2, defined in Section 9.3). The efficacy for Cohort 1 will be evaluated on the treated population set. A secondary analysis of efficacy will be performed combining the data pre- and post-Amendment 6, i.e. combining the data from participants who received PegIFN- $\alpha$ 2a but not JNJ-6379 in Cohort 1 with data of Cohort 2. The approach to combine data from the 2 cohorts will be described in detail in the Statistical Analysis Plan.

All efficacy summaries will be presented with descriptive statistics by cohort. If the endpoint is continuous, the descriptive statistics will include the number of participants, mean, standard deviation (SD), median, and range. If the endpoint is binary or categorical, the frequency distribution with the number and percentage of participants in each category will be calculated. For time-to-event variables, a summary table including number of participants included in the analysis, number of participants censored, 25th and 75th percentiles and median time-to-event will be shown by cohort. Graphic displays will also be used to summarize the data.

The baseline measurements are defined as the measurements taken closest to but before the first administration of study intervention on Day 1, unless otherwise specified.

\* Clopper-Pearson exact method is used.

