# 9.4.1.1. Primary Efficacy Endpoint (HBsAg Seroclearance 24 Weeks After Completion of Consolidation Phase Treatment)

The primary efficacy endpoint, the proportion of participants with HBsAg seroclearance 24 weeks after stopping all study interventions of the consolidation phase and without restarting NA treatment, will be summarized with the point estimate and its 90% CI using the Clopper-Pearson exact method.

All participants who do not achieve HBsAg seroclearance 24 weeks off-treatment post consolidation and/or require NA re-treatment within any time prior to FU Weeks 24 are considered treatment non-responders for the purpose of the primary endpoint analysis. If the HBsAg value at 24 weeks post consolidation is missing, the non-missing value closest to 24 weeks post consolidation within the window of 12 weeks prior/after will be used. In addition, participants who do not have data within the analysis window of  $\pm 12$  weeks around the Week 24 assessment will be defined as non-responder.

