## 5. EFFICACY

All efficacy data will be analyzed by cohort, combined cohort and overall, analysis phase and over time (when applicable). The primary analysis set will be the ITT analysis set for the primary efficacy endpoint, and the Treated analysis set for the rest efficacy endpoints. A secondary analysis set (combined cohort) will be performed combining the data from participants who received PegIFN- $\alpha$ 2a but not JNJ-6379 in Cohort 1 with data of Cohort 2 by analysis phase, the PegIFN- $\alpha$ 2a ITT analysis set will be used. This combined cohort is for the selected efficacy endpoints. The mTreated, mITT, and mPegIFN- $\alpha$ 2a ITT will be used if relevant difference between the sets exist (see Section 2.3). Selected efficacy endpoints will be also analyzed using the PP analysis set (see definition in Section 2.3). Efficacy assessments over time will be performed at the analysis time points defined in Section 2.1.

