### **5.3.2.1.2. HBsAg Sero clearance**

The proportion of participants achieving HBsAg seroclearance over time will be summarized by cohort and analysis phase. Separate analyses will be performed for participants who completed treatment as planned (at the end of consolidation phase), and regardless when treatment was stopped.

The proportion of participants with HBsAg seroclearance at the end of consolidation treatment will be tabulated by cohort.

The proportion of participants with HBsAg seroclearance will be evaluated at all off-treatment time points, respectively, after stopping all study interventions and without restarting NA treatment. In an additional summary, these proportions will be calculated with the denominator including only on those participants who have reached the off-treatment timepoint, and have stopped all interventions including NA and have not restarted NA prior to the timepoint of interest.

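### The Cohort 2 primary set called ITT omits anyone who stops during the 36-week induction, and a 5% rule can replace it with a set that drops pandemic-related losses

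*SAP*

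**What the plan says.** **Primary set.** The Protocol synopsis (Efficacy Analyses) says participants "who received at least 1 dose of consolidation phase study intervention within this ISA will be included in the ITT population", and makes that population of Cohort 2 the primary set. SAP 2.3 defines the set as "All participants who were randomized or enrolled and who received at least 1 dose of consolidation phase study intervention within this ISA", and Protocol 9.3 has the same requirement for a consolidation dose. SAP section 5 states: "The primary analysis set will be the ITT analysis set for the primary efficacy endpoint, and the Treated analysis set for the rest efficacy endpoints". For the other cohort, Protocol 9.4.1 says: "The efficacy for Cohort 1 will be evaluated on the treated population set".

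**Early stoppers.** Protocol 7.1: "If a participant prematurely (before the end of the consolidation phase) discontinues JNJ-3989, the participant will enter the 48-week follow-up phase". They do not pass through consolidation.

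**Missing data.** Protocol 9.4.1.1 takes the value nearest to follow-up (FU) Week 24 within 12 weeks either side. After that, "participants who do not have data within the analysis window of" ±12 weeks are non-responders. No exception is made for pandemic reasons.

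**Replacement rule.** SAP 2.3 defines mITT and mTreated, neither of which is in Protocol 9.3. mITT removes participants who, for pandemic-related reasons, left the study before FU Week 24 or had no assessment for the primary endpoint. If ITT and mITT differ by 5% or more of the total population, "then, the mTreated, and mITT will be used"; ITT and Treated apply only below that threshold. SAP section 5 repeats the rule.

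**The concern.** The primary objective is the efficacy of JNJ-3989 + PegIFN-α2a + NA as a regimen, and the first 36 of its 48 treatment weeks are induction. A set that requires a consolidation dose measures success among those who got through induction. That is a different quantity, and the label ITT hides the difference. In a single-arm study with no hypothesis test, the rate and its interval are the whole result, so the denominator matters directly. Under the protocol the two cohorts are also reported on different denominators.

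The 5% rule is a separate problem. It is prespecified, but its outcome is known only after missingness has been observed. It replaces the primary set where a sensitivity analysis would do. mTreated carries the problem further: a participant with no primary assessment for pandemic reasons is removed from endpoints at every other visit, where data may exist.

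**Working it through.** **Inputs.** Cohort 2 N = 33, 10% dropout, 30 expected with data, 15 responders, total sample about 60 (Protocol 9.2); two-sided 90% Clopper-Pearson interval (Protocol 9.4.1.1). The documents do not say how many dropouts fall in induction or how many losses are pandemic-related, so both are shown as ranges.

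**Formula.** For x responders of n: lower = Beta(0.05; x, n−x+1) quantile; upper = Beta(0.95; x+1, n−x) quantile.

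**Step 1, the plan's own figure.** 33 × 0.9 = 29.7, rounded to 30. 15/30 gives 0.339–0.661, width 0.322, as Protocol 9.2 states.

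**Step 2, induction stoppers left out.** Keep 15 responders and let 0 to 3 of the 3 planned dropouts fall in induction.

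| Stoppers in induction | ITT rate | 90% CI | Above 15/33 (points) |
|---|---|---|---|
| 0 | 15/33 = 45.5% | 0.305–0.611 | 0 |
| 1 | 15/32 = 46.9% | 0.315–0.627 | 1.4 |
| 2 | 15/31 = 48.4% | 0.327–0.643 | 2.9 |
| 3 | 15/30 = 50.0% | 0.339–0.661 | 4.5 |

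The Treated rate is 15/33 in every row, because a stopper cannot respond as the endpoint is worded.

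**Step 3, a low response rate.** The rationale for SAP Amendment 4 reports a single participant who met the NA completion criteria and stopped NA at consolidation Week 12. With one responder, 1/30 = 3.3% against 1/33 = 3.0%, a gap of 0.3 points.

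**Step 4, the switch trigger.** SAP 2.3 does not define the total population. 5% of 60 = 3.0, so 3 participants; 5% of 33 = 1.65, so 2 participants.

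**Step 5, effect of the switch.** Take ITT = 33, 15 responders and 3 pandemic losses.

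- Against missing = non-responder, none of the 3 counts as a responder, so mITT gives 15/30 = 50.0% against 45.5%: +4.5 points.
- Against the ±12-week rule (LOCF in the SAP), let k of the 3 have a usable value showing response. mITT gives (15−k)/30:

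| k | mITT rate | Difference from 45.5% (points) |
|---|---|---|
| 0 | 50.0% | +4.5 |
| 1 | 46.7% | +1.2 |
| 2 | 43.3% | −2.1 |
| 3 | 40.0% | −5.5 |

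Against the protocol's own rule, then, the direction is not fixed, because mITT also drops people who have a usable value.

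**The case against.** The strongest reply is that the set is disclosed and consistent. Both documents require a consolidation dose, and the endpoint is itself timed from the end of consolidation, so set and endpoint match. The study is an exploratory proof of concept. Treated-set results are coming anyway: SAP 5.3.2 uses the Treated set for secondary endpoints, and SAP 5.3.2.1.2 says "The proportion of participants with HBsAg seroclearance will be evaluated at all off-treatment time points". SAP 4.1 tabulates participants not treated in each phase, so a reader could rebuild the denominator.

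Some of this stands:

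- The induction exclusion is in the protocol too, so it is a fault of design and labelling and not an SAP departure. Only the switch is new in the SAP.
- The stopper's non-response is definitional. Such a person may stop NA and clear HBsAg, and SAP 5.3.1.1.3 counts that separately; the primary endpoint cannot.
- Someone who completes induction but cannot take PegIFN-α2a continues the other treatment and stays in ITT.
- SAP section 4 says the modified sets may be used, which is softer than 2.3 and section 5.
- Most of the fall in the lower bound from 0.34 to 0.30 comes from the lower rate. Near 50% of 33, 16/33 gives 0.333–0.639, and its width of 0.307 is slightly narrower than 0.322.
- SAP 5.2.2.1 lists three missing-data methods and ranks none, so the set alone does not settle the headline result.

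None of it removes the point. Consistent wording does not make a post-induction set intention-to-treat, and the planned Treated-set analyses are subject to the same switch to mTreated.

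**Conclusion.** Both parts hold. The induction exclusion biases the Cohort 2 rate in one direction only, by 0 to 4.5 points at the plan's 15 responders and by at most 0.3 points with one responder. The range assumes 33 enrolled, 3 dropouts and an unknown split between phases. The switch can be triggered by 2 or 3 participants. It raises the rate against missing = non-responder and may move it either way against the ±12-week rule. The realised effect may well be small, given what SAP Amendment 4 reports. This is a cheap improvement: the gain is a correctly named denominator that is fixed before the data are seen.

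**What to change.** - **Protocol 9.3 and 9.4.1, SAP 2.3 and 5:** analyse the Cohort 2 primary endpoint on the Treated set, as Protocol 9.4.1 does for Cohort 1. Participants who never enter consolidation, or who have no value within ±12 weeks of FU Week 24, count as non-responders under Protocol 9.4.1.1. State that this rule is the primary missing-data method.
- **Name:** call the present ITT set 'entered consolidation' and keep it as supportive.
- **5% rule:** delete it. Report mITT only as a sensitivity analysis of the FU Week 24 endpoint, and do not use mTreated for other visits.
- **Protocol 9.2:** restate precision on 33 (15/33: 0.305–0.611, width 0.306).

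The cost is wording in both documents, including an amendment to the protocol's primary population, and one changed denominator. No data or visits are added. The headline rate and stated lower bound become slightly less favourable (about 0.30 instead of 0.34 at 15 responders).

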## 2.4. On-treatment and off-treatment periods

The on-treatment period begins with the first drug intake date and finishes with the maximum between:

- Last dose of NA + 2 days,
- Last dose of PegIFN  $\alpha$ 2a+ 10 days,
- Last dose of JnJ-3989 + 28 days.

The off-treatment period stops if the NA re-treatment starts.

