### Amendment 4:

Overall rationale of this Amendment:

This administrative amendment incorporates additional clarifications on subgroups and analyses which have been documented in the Data Presentation Specification.

Clarifications, Additions, Corrections		
Section Number and Name	Description of Change	Rationale
2.5.1 Subgroup for Efficacy Analyses	
Addition of the following subgroups:
 
 
- Immune tolerant
 
- Peg-responder definition #1
 
- Peg-responder definition #2
 
 
Removal of the following subgroups:
 
 
- NA treatment history
 
- Fibrosis stage
 
- Sex
 
- Geographical region
 
- Duration of exposure to antigens
 
 
Regrouping of the age categories: >30 years - ≤45 years, >45 years - ≤55 years in one category: >30 years
	To allow for a more focused assessment of factors impacting efficacy outcomes and reduce the overall number of outputs
5.4.1.3.1. Association Between Baseline Characteristics/Viral Blood Markers and Selected Efficacy Variables	Removal of the correlation analyses between off-treatment HBV markers and other endpoints	Insufficient data for correlation analysis since there is only one patient who has met the NA treatment completion criteria and stopped NA (i.e. off-treatment) at CW12.
5.4.1.3.1. Association between several endpoints	The title has been changed to reflect the analyses detailed in this subsection.	To characterize association between changes in viral and safety markers during PegIFN administration.

Clarifications, Additions, Corrections		
Section Number and Name	Description of Change	Rationale

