- Per Protocol Amendment #5, participants will be randomized at baseline in a 1:1 ratio to one of the following intervention arms: JNJ-3989+JNJ-6379+NA (Cohort 2, Arm 3) or JNJ-3989+NA (Cohort 2, Arm 4). Upon completion of the 36-week induction phase, all participants will enter the 12-week consolidation phase during which they will have PegIFN- $\alpha$ 2a added to their treatment regimen.

**Note:** With the implementation of an urgent safety measure, as described in Protocol Amendment 6, participants previously enrolled had to immediately switch to the new study design. Participants had to stop JNJ-6379 treatment immediately and continue with JNJ-3989+NA treatment up to the end of the induction phase and will then enter the 12-week consolidation phase during which they will have PegIFN- $\alpha$ 2a added to their treatment regimen.

- As of Protocol Amendment 6, the study will continue as a single-arm study (JNJ-3989+NA+PegIFN- $\alpha$ 2a). All newly enrolled participants will receive JNJ-3989+NA for 36 weeks (induction phase) and will then enter the 12-week consolidation phase during which they will have PegIFN- $\alpha$ 2a added to their treatment regimen.

At the end of the consolidation phase, all participants will enter the FU phase and stop treatment with JNJ-3989+PegIFN- $\alpha$ 2a. If NA treatment completion criteria (HBsAg  $<10$  IU/mL, and HBeAg-negative, and HBV DNA  $<$ LLOQ, and ALT  $<$ 3x upper limit of normal [ULN]) have been met at consolidation Week 12, NA will also be stopped at the next scheduled visit (ie, FU Week 2), otherwise NA treatment will continue during the complete FU phase. Participants will be monitored closely during the 48-week FU phase and should restart NA treatment in accordance with the NA re-treatment criteria.

As of protocol Amendment #6, study intervention consists of:

- 200 mg JNJ-3989 (SC injection Q4W)
- 245 mg tenofovir disoproxil (tablets qd) – **Note:** tenofovir disoproxil may be supplied as fumarate or maleate
- 180 µg PegIFN- $\alpha$ 2a (SC injection, QW)

**Note:** Most participants enrolled before Protocol Amendment #6 was in effect, also received 250 mg JNJ-6379 (tablets qd) as part of their study intervention.

All participants will be considered to have completed the study if they have completed the assessments of the end-of-study (EOS) visit (ie, FU Week 48).

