The start date of a confirmed on-treatment biochemical flare is defined as the first date of two consecutive visits with ALT and/or AST  $\geq 3x$  ULN and  $\geq 3x$  nadir (i.e., lowest value observed up to the time point of meeting the biochemical flare criteria) while the participant receives any of the study interventions. The end date of the same on-treatment biochemical flare is defined as the first date when there is a 50% reduction from the peak ALT and/or AST level &  $< 3x$  ULN, regardless of stopping the study interventions.

- 1 (Yes) = confirmed\*\* ALT and/or AST  $\geq 3x$  ULN and  $\geq 3x$  nadir (i.e., lowest value observed on-treatment period up to the time point of meeting the biochemical flare criteria)
- 0 (No) = otherwise

d) **Clinical flare** is defined as follows:

A clinical flare occurs either when a virologic flare and biochemical flare overlap in time or when a biochemical flare starts within 4 weeks following the end of a virologic flare. The start date of a clinical flare is defined as the minimum start date of the virologic flare and the biochemical flare. The end date of a clinical flare is defined as the maximum end date of the virologic flare and biochemical flare, i.e., the later date between HBV DNA returns to  $\leq 200$  IU/mL and 50% reduction from the peak ALT and/or AST level &  $< 3x$  ULN .

- 1 (Yes)= confirmed\*\* HBV DNA  $>$  peak threshold and confirmed\*\* ALT and/or AST  $\geq 3x$  ULN and confirmed\*\*  $\geq 3x$  nadir (i.e., lowest value observed during off-treatment period up to the time point of meeting the flare criteria).
- 0 (No) = otherwise

\*\* Confirmed means that the criterion should be fulfilled at 2 or more consecutive time points or at the last observed time point.

The virologic and clinical flares will be assessed only off-treatment, while biochemical flares will be identified on treatment and off treatment, respectively. On-treatment virologic flares are described as virologic breakthrough in Section 5.3.1.1.8. On-treatment will be defined as the time period in which the participant receives any of the study interventions. Off-treatment will be defined as the period after stopping all study interventions (including NA). In addition, the proportion of subjects with off-treatment virologic flares, ALT and clinical flare for subjects who met NA treatment completion criteria and stopped NA will be shown.

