### **5.3.1.2. Values and Changes Over Time Endpoints**

#### **5.3.1.2.1. HBsAg, HBeAg, HBV DNA and ALT**

Actual values (original unit and  $\log_{10}$  transformed values) and changes from baseline ( $\log_{10}$  transformed values) over time in HBsAg, HBeAg (for participants HBeAg positive at baseline only), HBV DNA and ALT (actual values only) will be evaluated.

Change from baseline is defined as follows: value at a given time point minus baseline value.

The change from baseline value to nadir (i.e., maximum decrease for each participant) in HBsAg, HBeAg and HBV DNA will be evaluated at three intervals: on-treatment nadir, during follow-up nadir, and entire study duration nadir.

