### 7.1. Time Points and Samples

When analyzing sequencing data, the focus will be on genetic variants at

- Time Point of Sequence at Baseline (BLSEQ): Last available pre-first dose time point in the study with sequence data available
- Time Point of Sequence at End of Study Agent (last available on-treatment time point, with a specific focus on subjects not meeting the NA treatment completion criteria)
- Time Point of Sequence at Virologic Breakthrough: time point with sequence data available closest to the time point of virologic breakthrough (FTPT) (See Section 5.3.1.1.8 for virologic breakthrough definition)
- Time Point of Sequence at Virologic Flare: time point with sequence data available closest to the time point of Virologic flare (See Section 5.3.1.1.9 for virologic flare definition)
- Time Point of Sequence at End of Study (ESSEQ): last available off-treatment post-baseline time point in the study with sequence data available
- Time Point of Sequence at Re-treatment during Post-treatment Follow-up: time point with sequence data available closest to time point where re-treatment criteria is met (See Section 5.3.1.1.2.2)
- Aggregated Post-Baseline Study Period (ASSEQ): entire post-baseline study period, aggregate of all available time points in the study with sequence data available
- Aggregated Post-Baseline Treatment Period (ATSEQ): entire post-baseline treatment period, aggregate of all available post-baseline time points during the treatment phase with sequence data available
- Aggregated Off-treatment follow-up period: entire period with no drug taken, aggregate of all available time points during the off-treatment period with sequence data available

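### Background NA sets the end of the SAP's on-treatment period, so in NA continuers the on-treatment nadir duplicates the entire-study nadir and the End of Study Agent sequence can fall as late as FU Week 48

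*SAP*

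**What the plan says.** SAP 2.4 fixes one on-treatment period for the whole plan: "The on-treatment period begins with the first drug intake date and finishes with the maximum between" three dates. These are "Last dose of NA + 2 days", the last PegIFN dose plus 10 days, and "Last dose of JnJ-3989 + 28 days". The section closes by saying that the off-treatment period ends if NA is restarted.

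SAP 2 separates two terms. Study treatment includes NA. Study agent means JNJ-3989 and PegIFN (plus JNJ-6379 before Protocol Amendment 6) and does not include NA.

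Under SAP 1.2, NA stops at FU Week 2 if the completion criteria were met at consolidation Week 12; "otherwise NA treatment will continue during the complete FU phase". SAP Amendment 4 gives the outcome: "there is only one patient who has met the NA treatment completion criteria and stopped NA".

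Two sets of outputs use the word on-treatment without a definition of their own:

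- **Nadirs.** SAP 5.3.1.2.1 evaluates the maximum decrease in HBsAg, HBeAg and HBV DNA over three intervals: "on-treatment nadir, during follow-up nadir, and entire study duration nadir". SAP 5.3.2.2.1 tabulates and box-plots the changes to nadir. SAP 5.4.1.2.1 repeats the three intervals for HBV RNA and HBcrAg, split by whether NA was stopped.
- **Sequencing.** SAP 7.1 lists "Time Point of Sequence at End of Study Agent (last available on-treatment time point", and the same bracket singles out participants who miss the NA completion criteria. SAP 7.5.2 then plans end-of-treatment variant tables in that group and, optionally, a table of return to baseline.

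**The concern.** A rule that takes the latest of three dates hands the end date to whichever drug lasts longest. Here that is the background drug, which most participants take for the whole of follow-up. The nadir split was presumably meant to separate what happened under JNJ-3989 and PegIFN from what happened afterwards. For a participant who continues NA it cannot do so, because the on-treatment interval is the whole study.

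In sequencing, the label and the definition disagree. The label names the end of drugs that exclude NA; the definition follows NA. The disagreement bites in exactly the group that SAP 7.1 says it wants to look at. What is at stake is how variants selected by JNJ-3989 are reported. A frequency table headed End of Study Agent could describe virus sampled long after those agents stopped, when variants may have reverted.

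**Working it through.** **1. Check the timeline.** Screening 4 to 6 + induction 36 + consolidation 12 + follow-up 48 = 100 to 102 weeks, as Protocol 4.1 states. With a 60-week induction, 6 + 60 + 12 + 48 = 126 weeks, also as stated.

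**2. Last scheduled doses, Cohort 2.** The last JNJ-3989 dose is at consolidation Week 8, C Day 57 (Protocol 1.3.2). Twelve weekly PegIFN doses (the count in SAP 4.7) starting on C Day 1 end on C Day 1 + 11 × 7 = 78. NA in a continuer runs to FU Week 48, which is FU Day 337.

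**3. End of period if only JNJ-3989 and PegIFN count.** max(57 + 28, 78 + 10) = max(85, 88) = C Day 88. In study time, 36 × 7 + 88 = 340 days, or 48.6 weeks.

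**4. End of period as written.** FU Day 1 can be anchored to the last PegIFN dose (C Day 78; Protocol 1.3.2 counts follow-up visits from the last dose) or to the day after the consolidation Week 12 visit (C Day 86; SAP Table 1).

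| | Anchor C Day 78 | Anchor C Day 86 |
|---|---|---|
| FU Week 48 (anchor + 336) | C Day 414 | C Day 422 |
| Last NA dose + 2 days | C Day 416 | C Day 424 |
| Study week, (252 + C Day)/7 | 95.4 | 96.6 |
| Excess over C Day 88 | 328 days (46.9 weeks) | 336 days (48.0 weeks) |

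**5. Nadirs.** For a continuer, on-treatment runs from first dose to the last visit, which is also the entire-study interval. The minimum over two identical intervals is identical. The follow-up interval lies inside the on-treatment one, so a nadir reached in follow-up is also labelled on-treatment.

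**6. Sequence time point.** Consolidation Week 12 (C Day 85) and FU Week 48 are both scheduled sequencing visits. The latest possible End of Study Agent sample is therefore 414 − 85 = 329 days (47.0 weeks) to 422 − 85 = 337 days (48.1 weeks) after consolidation Week 12. Whichever sample is chosen, it is by construction the last sequence that a continuer has. If the end-of-treatment tables in SAP 7.5.2 use this time point, as the shared focus on non-completers suggests, nothing later exists to show a return to baseline. The End of Study time point in SAP 7.1 does not help, because it asks for an off-treatment sample and a continuer has none.

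**7. How many.** The number treated is not given. With one stopper, the share of continuers is (N − 1)/N: 98.3% at the target of 60, 97.0% at 33, 96.4% at 28. These are illustrations. They ignore early discontinuations, and some participants who stop JNJ-3989 early may also stop NA (Protocol 7.1).

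**The case against.** Counting NA is deliberate. NA is study treatment, and SAP 5.3.1.1.8 and 5.3.1.1.9 repeat the NA-inclusive rule for breakthrough and flares, where it is the right one. That stands. The defect lies only in reusing the period for the nadirs and for a time point named after the study agents.

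Several stronger readings are tempting, and the documents do not support them:

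- *The end-of-agent sequence is taken a year late in everyone.* The 47 to 48 weeks is a maximum. The rule takes the last available sequence, and sequencing depends on HBV DNA level and the virologist's request. A suppressed participant's last sequence may be much earlier.
- *The end-of-agent variant data are lost.* SAP 7.5.3 still lists variants at the end of consolidation for all participants. One set of frequency tables is mistimed.
- *All three nadirs collapse, so the effect of the agents cannot be seen.* Two coincide; the follow-up nadir has its own start in SAP Table 1. SAP 5.3.2.2.1 also gives values and changes by phase and at end of consolidation.
- *Re-treatment swallows the off-treatment gap.* Read literally, the last NA dose falls after a restart. But the closing line of SAP 2.4 presupposes an off-treatment period before it, and about one participant could be concerned. This calls for clarification only.
- *Flare reporting is faulty.* Nothing in the flare definitions shows this.

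A further objection concerns the remedy. In earlier data mean HBsAg reached its nadir 8 weeks after the last JNJ-3989 dose (Protocol 2.2.2.1). Applied here, that is C Day 57 + 56 = 113, which is 25 days beyond C Day 88. An agent-based window could therefore close before the HBsAg nadir. This is fair, and it is a reason to keep the follow-up nadir beside the on-agent one.

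**Conclusion.** Wrong as written, as a time-point definition; low severity. For participants who continue NA through follow-up, the on-treatment nadir repeats the entire-study nadir. The End of Study Agent sequence may be drawn up to 47 to 48 weeks after consolidation Week 12, with no later sample for the return-to-baseline table. On the Amendment 4 statement, this applies to all but one of those who reach follow-up on NA.

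The size rests on the scheduled Cohort 2 doses, on NA being taken to FU Week 48, and on one stopper. Participants who leave early do not reach FU Week 48, but if they took NA until leaving, their two nadirs still coincide.

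A reader might infer a threat to the main results. There is none: the primary endpoint, the by-phase summaries and the end-of-consolidation variant listing do not use this period. There is no formal hypothesis, and the affected outputs are descriptive or exploratory.

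**What to change.** - Add an on-study-agent period to SAP 2.4: first dose to the later of last JNJ-3989 + 28 days and last PegIFN + 10 days. The end of consolidation in SAP Table 1 is an acceptable alternative.
- Use it for the on-treatment nadir in SAP 5.3.1.2.1 and 5.4.1.2.1, and for the End of Study Agent / End of Treatment sequence in SAP 7.1 and 7.5.2. Later samples can then show reversion.
- Keep the follow-up nadir as a separate summary, since the HBsAg nadir may come after the cut.
- Keep the NA-inclusive period for virologic breakthrough and flares, unchanged.
- State that last dose of NA means the last dose before any NA re-treatment.

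The cost is SAP wording and one derived period flag. No new data, visits or treatment changes are needed.
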